5.2 ASSESSMENT OF SAFETY

The primary and secondary endpoints of safety will be based on data at timepoints defined in [Section 2.1.2](#) and [Section 2.1.3](#). The 52 weeks time point will not be available for all patients, depending on the time of enrolment into the study.

5.2.1 Physical examination

A complete physical examination will be performed at the time points specified in the Flow Chart. It includes at a minimum general appearance, neck, lungs, cardiovascular system, abdomen, extremities, and skin.

The results must be included in the source documents available at the site.

All abnormal findings at baseline will be recorded on the Baseline Condition CRF page. New abnormal findings or worsening of baseline conditions detected at the subsequent physical examinations, if judged clinically relevant, will be recorded as adverse events on the appropriate CRF page.

5.2.1.1 Body weight

Measurement of body weight will be performed at the time points specified in the [Flow Chart](#). If possible, the patient's weight in the 2 years before screening (Visit 1) will be recorded, in order to detect any potential change in growth velocity over time.

Body weight measurements will be recorded in the source documents and transcribed into the CRF.

These measurements will be used to assess safety, and to assign the proper dose of trial medication at randomisation and subsequent IMP dispensing visits.

5.2.1.2 Height, leg length

Close monitoring of standing and sitting heights and leg length will be conducted at the time points specified in the Flow Chart and footnotes. If possible, the patient's height in the 2 years before screening (Visit 1) will be recorded, in order to detect any potential change in growth velocity over time.

At each time point, height, sitting height will be assessed three times, and the average of the 3 measurements will be taken. Height and sitting height will be assessed using a stadiometer. The stadiometer should be calibrated at regular intervals (see ISF for further instructions). The sitting height should be standardized and calibrated. Leg length will be assessed by measuring the distance between the anterior iliac spine and the medial malleolus. This will be measured three times on each leg, and the average of the 3 measurements will be taken.

These measurements will be recorded in the source documents available at the site and the average transcribed into the CRF.

These measurements will be used to assess safety and be periodically reviewed by the Safety Monitoring Committee.

5.2.2 Vital signs

Vital signs will be evaluated at the time points specified in the Flow Chart, prior to blood sampling.

This includes systolic and diastolic blood pressure and pulse rate (electronically or by palpation count for 1 minute) in a seated position after 5 minutes of rest. See also [Appendix 10.4](#) for details.

The results must be included in the source documents available at the site.

All abnormal findings at baseline will be recorded on the Baseline Condition CRF page. New abnormal findings or worsening of baseline conditions detected at the subsequent physical examinations, if judged clinically relevant, will be recorded as adverse events on the appropriate CRF page.

5.2.3 Safety laboratory parameters

Safety laboratory parameters to be assessed are listed in [Table 5.2.3: 1](#). For the sampling time points please see the [Flow Chart](#).

All analyses will be performed by a central laboratory, the respective reference ranges will be provided in the ISF.

Patients do not have to be fasted for the blood sampling for the safety laboratory.

Instructions regarding sample collection, sample handling/ processing and sample shipping are provided in the Laboratory Manual in the ISF.

The central laboratory will send reports to the investigator. It is the responsibility of the investigator to evaluate the laboratory reports. Clinically relevant abnormal findings as judged by the investigator will be reported as adverse events (please refer to [Section 5.2.7.1.1](#)).

In case the criteria for hepatic injury are fulfilled, a number of additional measures will be performed (please see [Section 5.2.7.1.4](#) and the DILI Checklist provided in the electronic Data Capture (eDC) system. The amount of blood taken from the patient concerned will be increased due to this additional sampling.

The central laboratory will transfer the results of the analysis to the sponsor.

Table 5.2.3: 1 Safety laboratory tests at regular site visits

The laboratory tests at regular site visits will include:

| Category | Laboratory test |
|--------------|---|
| Haematology | Red blood cell count (RBC) Haemoglobin (Hb) Haematocrit (Hct) Mean corpuscular volume White blood cell count including differential count Platelet count |
| Biochemistry | Aspartate aminotransferase (AST) Alanine transaminase (ALT) Gamma-glutamyl transferase (GGT) Alkaline phosphatase (ALK) Creatine kinase (CK) Lactate dehydrogenase (LDH) Total protein Total bilirubin Creatinine Glucose (non fasting, V1 and V2 only) Uric acid Thyroid stimulating hormone β-HCG (at all visits requiring blood sampling for laboratory tests until EoT– in all and only female patients)* |
| Electrolytes | Sodium Potassium Calcium Chloride Inorganic phosphorus |
| Coagulation | International normalized ratio (INR) Activated partial thromboplastin time (aPTT) Prothrombin time (PT) |
| Urinalysis | pH, glucose, erythrocytes, leukocytes, protein, nitrite (semi-quantitative measurements; -, +, ++, +++) |

*Pregnancy test is required in all female patients every 4-6 weeks, either at home or at site. β-HCG test on blood will be conducted at all visits until end of treatment on blood collected for laboratory tests. Locally provided urine dipstick pregnancy tests will be dispensed for use between clinic visits starting from Visit 4. A urine dipstick pregnancy test will be conducted at the Follow-up Visit (if acceptable) and test results will be documented in the patient's records. In case of positive results, procedures defined in [Section 5.2.7.2.3](#) should be followed.

Table 5.2.3:2 Safety laboratory tests at intermediate ‘a’-visits

The laboratory tests at intermediate ‘a’-visits will include:

| Category | Laboratory test |
|--------------|---|
| Biochemistry | Total protein, creatinine, electrolytes and liver function (AST, ALT, GGT, alkaline phosphatase, and total bilirubin) |
| Urinalysis | pH, glucose, erythrocytes, leukocytes, protein, nitrite (semi-quantitative measurements; -, +, ++, +++) |

At ‘a-Visits’, safety blood, and urine samples will be collected and submitted to the central laboratory if needed for additional safety monitoring at the discretion of the Investigator (see cautionary notes under [Section 4.2.2.1](#) for additional safety monitoring).

The samples may be collected at the office of a local doctor using trial specific lab kits that will be sent to a central laboratory for analyses. These kits will be provided to patients at study visits as applicable.

A maximum total amount of approximately 38 mL blood will be taken for standard safety laboratory tests during the course of Part A. In Part B, a maximum total amount of approximately 44 mL blood will be taken for standard laboratory (this is based on a 76-week duration of Part B, but it might be less depending of the time the patient will stay in Part B).

Creatinine clearance will be calculated based on serum creatinine according to Schwartz formula [[R10-0828](#), [R11-4789](#)] (see [Appendix 10.2](#)).

If laboratory values indicate abnormality, adequate and more frequent blood sampling may be performed at the discretion of the Investigator.

In case of liver function value elevations, close monitoring must be ensured by the Investigator. Refer to [Section 4.1.2](#) for monitoring elevations and [Section 3.3.4](#) for withdrawal criteria.

Laboratory analysis will be done using central laboratory services. Blood sampling will be conducted using materials and techniques suitable for the paediatric population. Venous whole blood will be collected in appropriate syringes provided by the sponsor through the assigned central laboratory. All efforts should be made to use the lowest amount of blood per sample as technically possible, e.g. by using special paediatric collection systems.

Details regarding centrifuge, processing, storage and shipment of samples will be determined by the central laboratory in accordance with the sponsor. The Investigators will be informed and instructed by the central laboratory and detailed documentation will be included in the ISF.

5.2.4 Electrocardiogram

Resting 12 lead Electrocardiograms (ECGs) will be conducted at sites using their own equipment.

The 12-lead ECGs must be administered by a qualified technologist and results will be recorded as scheduled in the [Flow Chart](#). The investigator or a designee will evaluate whether the ECG is normal or abnormal (rate, rhythm and repolarization changes have to be evaluated, compared to previous tracings) and assess clinical relevance. ECGs may be repeated for quality reasons and a repeated recording used for analysis.

Additional ECGs may be recorded for safety reasons. Dated and signed printouts of ECG with findings should be documented in patient's medical record.

Clinically relevant abnormal findings will be reported either as baseline condition (if identified at the screening visit) or otherwise as AEs and will be followed up and/or treated as medically appropriate.

5.2.5 Assessment of pathological findings of epiphyseal growth plate

MRI assessments of the distal femur and proximal tibia will be conducted as primary bone imaging methodology to assess the potential risk of skeletal toxicity of nintedanib in the growing population. In each patient the same side should be imaged at each assessment. In situations in which MRI cannot be performed, especially if sedation is required, x-rays of the distal femur and proximal tibia (AP knee radiograph) will be conducted as secondary methodology.

MRIs/x-rays of growth plates will be conducted in all patients who qualified for randomisation at baseline. Imaging follow-up will be conducted only in patients with open physes, at 3 months, 6 months, 9 months, 12 months after start of trial medication, and every 6 months thereafter until end of the study or closure of physes.

The same acquisition protocol specifications should be used for all MRIs/x-rays of growth plates. Details will be provided in the image acquisition guideline for bone safety monitoring available in the ISF. Whenever possible, scans should be completed on the same scanner and by the same radiologist at each site. Scans will be transferred for central review and stored at the sponsor facilities or by an external vendor.

MRI/x-ray assessments will be evaluated in a centralised manner by a blinded external expert in radiology. In addition, all MRI/x-ray assessments and height measurements (see [Section 5.2.1.2](#)) will be periodically reported to the Safety Monitoring Committee.

5.2.6 Assessment of pathological findings on dental examination or imaging

Dental examination (clinical examination) and imaging (panoramic x-ray) will be conducted in all patients who qualified for randomisation to assess the potential severe/irreversible effects of nintedanib on teeth in the study population.

Dental examination will be conducted at baseline. Follow-up will be conducted at 12 weeks, 24 weeks, 36 weeks, 52 weeks after start of trial medication, and every 24 weeks thereafter until end of the study.

A panoramic x-ray will be conducted at baseline. Dental imaging follow-up will be conducted at 24 weeks, 52 weeks after start of trial medication, and every 48 weeks thereafter until end of the study.

Dental examination will be conducted at the investigational site or external facility by a dentist.

Panoramic x-rays will be conducted at the investigational site or external facility. The same specifications will be used for all panoramic x-rays. Details will be provided in the image acquisition guideline for teeth safety monitoring available in the ISF. Whenever possible, panoramic x-rays should be completed on the same device. Dental cone beam computed tomography can be conducted only in case panoramic x-rays cannot be performed, as far as it allows the same assessments, it is conducted according to the image acquisition guideline, and the same device is used consistently in the same patient.

X-rays will be transferred for central review and stored at the sponsor facilities or by an external vendor.

Panoramic x-rays will be evaluated in a centralised manner by a blinded external expert in paediatric dentistry.

Dental examination and imaging will be periodically reported to the Safety Monitoring Committee.

5.2.7 Assessment of adverse events

5.2.7.1 Definitions of AEs

5.2.7.1.1 Adverse event

An AE is defined as any untoward medical occurrence in a patient or clinical investigation subject administered a medicinal product and which does not necessarily have to have a causal relationship with this treatment.

An AE can therefore be any unfavourable and unintended sign (including an abnormal laboratory finding), symptom, or disease temporally associated with the use of a medicinal product, whether or not considered related to the medicinal product.

The following should also be recorded as an AE in the CRF and BI SAE form (if applicable):

- Worsening of the underlying disease (including acute ILD exacerbations) or of other pre-existing conditions;
- Pathological findings of epiphyseal growth plate on imaging;
- Pathological findings on dental examination or imaging;

- Changes in vital signs, ECG, physical examination (including changes in standing and/or sitting height, changes in leg length) and laboratory test results, if they are judged clinically relevant by the investigator.

If such abnormalities already exist prior to trial inclusion, they will be considered as baseline conditions and should be collected in the eCRF only.

5.2.7.1.2 Serious adverse event

A serious adverse event (SAE) is defined as any AE, which fulfils at least one of the following criteria:

- results in death,
- is life-threatening, which refers to an event in which the patient was at risk of death at the time of the event; it does not refer to an event that hypothetically might have caused death if more severe,
- requires inpatient hospitalisation or prolongation of existing hospitalisation,
- results in persistent or significant disability or incapacity,
- is a congenital anomaly / birth defect,
- is deemed serious for any other reason if it is an important medical event when based on appropriate medical judgement which may jeopardise the patient and may require medical or surgical intervention to prevent one of the other outcomes listed in the above definitions. Examples of such events are intensive treatment in an emergency room or at home for allergic bronchospasm, blood dyscrasias or convulsions that do not result in hospitalisation or development of dependency or abuse.

5.2.7.1.3 AEs considered “Always Serious”

In accordance with the European Medicines Agency initiative on Important Medical Events, Boehringer Ingelheim has set up a list of further AEs, which by their nature, can always be considered to be “serious” even though they may not have met the criteria of an SAE as defined above.

The latest list of “Always Serious AEs” can be found in the eDC system. A copy of the latest list of “Always Serious AEs” will be provided upon request. These events should always be reported as SAEs as described above.

Cancers of new histology and exacerbations of existing cancer must be classified as a serious event regardless of the time since discontinuation of the drug and must be reported as described in [5.2.7.2](#), subsections “AE Collection” and “AE reporting to sponsor and timelines”.

5.2.7.1.4 Adverse events of special interest

The term adverse events of special interest (AESI) relates to any specific AE that has been identified at the project level as being of particular concern for prospective safety monitoring and safety assessment within this trial, e.g. the potential for AEs based on knowledge from other compounds in the same class. AESIs need to be reported to the sponsor’s Pharmacovigilance Department within the same timeframe that applies to SAEs, please see [Section 5.2.7.2.2](#).

The following are considered as AESIs:

- adverse events relating to gastrointestinal perforation
- bleeding
- hepatic injury
- pathological findings identified on bone imaging
- stunted growth identified on dental imaging

Hepatic injury

In this trial protocol, signs of hepatic injury are defined as:

- ALT and/or AST ≥ 8 fold ULN
- ALT and/or AST ≥ 3 fold ULN and total bilirubin ≥ 2 fold ULN*
- ALT and/or AST ≥ 3 fold ULN and unexplained INR $> 1.5^*$
- ALT and/or AST ≥ 3 fold ULN and unexplained eosinophilia ($>5\%$)*
- ALT and/or AST ≥ 3 fold ULN and appearance of fatigue, nausea, vomiting, right upper abdominal quadrant pain or tenderness, fever and/or rash

*in the same blood draw sample.

These lab findings constitute a hepatic injury alert and the patients showing these lab abnormalities need to immediately stop the trial medication and be followed up according to the “DILI checklist” provided in the eDC system. The investigator is asked to collect requested information within 48 hours upon laboratory hepatic injury alert/notification.

In case of clinical symptoms of hepatic injury (icterus, unexplained encephalopathy, unexplained coagulopathy, right upper quadrant abdominal pain, etc.) without lab results (ALT, AST, total bilirubin) available, the investigator should make sure these parameters are analysed, if necessary in an unscheduled blood test. Should the results meet the criteria of hepatic injury alert, the procedures described in the DILI checklist should be followed.

5.2.7.1.5 Intensity (severity) of AEs

The intensity (severity) of the AE should be judged based on the following:

- Mild: Awareness of sign(s) or symptom(s) that is/are easily tolerated.
Moderate: Sufficient discomfort to cause interference with usual activity.
Severe: Incapacitating or causing inability to work or to perform usual activities.

The intensity (severity) of diarrhoea adverse events should be classified and recorded in the CRF according to the Common Terminology Criteria for Adverse Events (CTCAE) version 5 [R18-1357], [Table 5.2.7.1.5: 1](#).

Table 5.2.7.1.5: 1 CTCAE Categorization for diarrhoea

| CTCAE Grade | Diarrhoea |
|-------------|---|
| 1 | Increase of <4 stools per day over baseline |
| 2 | Increase of 4 to 6 stools per day over baseline |
| 3 | Increase of ≥ 7 stools per day over baseline; incontinence |
| 4 | Life threatening consequences |
| 5 | Death |

5.2.7.1.6 Causal relationship of AEs

Medical judgement should be used to determine whether there is a reasonable possibility of a causal relationship between the adverse event and the given study treatment, considering all relevant factors, including pattern of reaction, temporal relationship, de-challenge or re-challenge, confounding factors such as concomitant medication, concomitant diseases and relevant history.

Arguments that may suggest that there is a reasonable possibility of a causal relationship could be:

- The event is consistent with the known pharmacology of the drug.
- The event is known to be caused by or attributed to the drug class.
- A plausible time to onset of the event relative to the time of drug exposure.
- Evidence that the event is reproducible when the drug is re-introduced.
- No medically sound alternative aetiologies that could explain the event (e.g. pre-existing or concomitant diseases, or co-medications).
- The event is typically drug-related and infrequent in the general population not exposed to drugs (e.g. Stevens-Johnson syndrome).
- An indication of dose-response (i.e. greater effect size if the dose is increased, smaller effect size if dose is reduced).

Arguments that may suggest that there is no reasonable possibility of a causal relationship could be:

- No plausible time to onset of the event relative to the time of drug exposure is evident (e.g. pre-treatment cases, diagnosis of cancer or chronic disease within days / weeks of drug administration; an allergic reaction weeks after discontinuation of the drug concerned).
- Continuation of the event despite the withdrawal of the medication, taking into account the pharmacological properties of the compound (e.g. after 5 half-lives). Of note, this criterion may not be applicable to events whose time course is prolonged despite removing the original trigger.

- Additional arguments amongst those stated before, like alternative explanation (e.g. situations where other drugs or underlying diseases appear to provide a more likely explanation for the observed event than the drug concerned).
- Disappearance of the event even though the trial drug treatment continues or remains unchanged.

5.2.7.2 Adverse event collection and reporting

5.2.7.2.1 AE Collection

The investigator shall maintain and keep detailed records of all AEs in the patient files. The following must be collected and documented on the appropriate CRF(s) by the investigator:

- From signing the informed consent onwards until the individual patient's end of trial: all AEs (serious and non-serious) and all AESIs.
- After the individual patient's end of trial: the investigator does not need to actively monitor the patient for new AEs but should only report any occurrence of cancer and trial treatment related SAEs and trial treatment related AESIs of which the investigator may become aware of by any means of communication, e.g. phone call. Those AEs should be reported on the BI SAE form (see [Section 5.2.7.2.2](#)), but not on the CRF.

Vital Status Data Collection

Patients who discontinue trial medication prematurely, whose parents/legal guardians agree to be contacted further but do not agree to physical visits, should be followed up as described in [Section 3.3.4.1](#), withdrawal from trial treatment. From then on until the individual patient's end of the trial the investigator must report all deaths/fatal AEs regardless of relationship, and trial treatment related SAEs and trial treatment related AESIs the investigator becomes aware of.

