For each patient, the study period is from the signature of the informed consent by the parent(s)/legal guardian until the patient's last visit of the study. Adverse events will be collected during the entire study period and considered treatment-emergent from first study drug intake until 28 days after drug discontinuation.

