4.2 CHANGES

5. ENDPOINT(S)

In this section, more details are given regarding endpoints. Please note that for all endpoints and analyses, [Section 6.7](#) should be consulted for baseline value definition.

Please note, that due to the design of the study, not all time points will be available for all patients.

Handling of missing data points is described in [Section 6.6](#).

For endpoints where the “date of last contact” is utilized, the following will apply:

- The last contact date when the patient was known to be alive is defined as the latest date recorded in the electronic Case Report Form (eCRF) from the dates listed below (in case an Adverse Event date is planned to be imputed for the analysis, the imputed date will also be used for the definition of “date of last contact”):
 - Date of last visit (e.g. for spirometry), date of last reported Adverse Event (AE) (excluding censored dates), date of last reported concomitant treatment, date of last laboratory sample, date of last drug intake, date of last reported dose change / interruption, end of study participation date (as documented on the End of Study eCRF page if the reason for not completing the planned observation period is NOT “Death”), vital status date (from the vital status eCRF page if the patient is known to be alive) and the latest of vital status date / last successful contact date (from the End of Study eCRF page if the patient was lost to follow-up).

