7.8 SAFETY ANALYSIS

7.8.1 Adverse Events

Adverse events will be coded using the current Medical Dictionary for Regulatory Activities (MedDRA) version in use at BI at the time of database lock. The analyses of AEs will be descriptive in nature.

All analyses of AEs will be based on the number of patients with AEs and NOT on the number of AEs. To account for the variable length of exposure to treatment in both study periods tables will be presented including count and percentage of patients with AE and the incidence rates of AEs with time at risk and rate per 100 patient years. Please refer to [Section 7.8.1.1](#) for further details on the derivation of time at risk and exposure-adjusted incidence rates.

Since this study consists of a double-blind, placebo-controlled part and an open-label part with nintedanib treatment only, three treatment periods will be used for analysis and definition of “treatment-emergent”:

- 1. Double-blind period:** Analyses of AEs will be presented by treatment group and overall. Only adverse events with onset or worsening on or after date of treatment start until end of double-blind period (defined as the day before first intake of open-label nintedanib or last double-blind drug intake + residual effect period, whichever is earlier) will be considered as treatment-emergent and will be included in the analysis. Adverse events will be counted under the treatment as randomized for the double-blind period.
- 2. Nintedanib exposure period:** Analyses of AEs will be presented by randomized treatment group and overall. All adverse events with onset or worsening on or after first intake of nintedanib (double-blind or open-label period) until last intake of nintedanib (double-blind or open-label period) + residual effect period will be considered as treatment-emergent and will be included in the analysis.

3. Over the whole-trial: Analyses of AEs will be presented by treatment group and overall. All adverse events with onset or worsening on or after date of treatment start until last drug intake + residual effect period will be considered as treatment-emergent and will be included in the analysis. Adverse events will be counted under the treatment as randomized for the double-blind period.

In case an AE starts on first day of open-label treatment, it is assigned to the open-label period (and not to the double-blind period).

For further details on summarization of AE data, please refer to ([8](#), [17](#)).

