7.8.1.2 Exposure adjusted analysis of adverse events over the whole trial

Time at risk and incidence rates per 100 patient-years will be calculated based on the first onset of an AE in the trial.

Time at risk:

For a specific AE, the total AE time at risk [years] is defined as

$$\frac{\sum \text{Time at risk (days) across all contributing patients}}{365.25}$$

with for each subject the time at risk [days] is defined as follows:

- *Date of first onset of the AE – date of first study drug intake + 1 day* for patients with the specific AE,
- *End of time at risk – date of first study drug intake + 1 day* for patients without the specific AE.

The end of time at risk is defined as the minimum of

- end date of the double-blind, whole-trial and nintedanib exposure treatment period, respectively (incl. REP)
- date of last contact (for definition see [Sec. 5](#))
- date of death
- date of the (interim) database lock.

For the double-blind treatment period, end of time at risk is the day before start of open-label period, in case the patient started open-label treatment before end of double-blind REP.

AE incidence rate:

The AE incidence rate [1/100 patient-years (pt-yrs)] will be calculated as

$$\frac{100 \times (\text{Number of patients with specific AE})}{\text{Total specific AE time at risk [years]}}$$

The 95% confidence intervals for incidence rates are derived using the method described by Rothman and Greenland (2008) ([20](#)).

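### AE reporting may be cut back for early stoppers who decline visits, with no exception for the 28-day residual effect period that the analysis still counts as treatment-emergent

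*Protocol*

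**What the plan says.** **Collection.** The general rule in Protocol 5.2.7.2.1 asks for "all AEs (serious and non-serious) and all AESIs" from consent to the patient's end of trial. Under Vital Status Data Collection, the same section turns to patients who stop drug early and whose parents or guardians "agree to be contacted further but do not agree to physical visits". For them the duty changes: "the investigator must report all deaths/fatal AEs regardless of relationship, and trial treatment related SAEs and trial treatment related AESIs", so far as these come to notice. The period for this is worded as "From then on until the individual patient's end of the trial". No start date is given and the residual effect period is not mentioned.

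**Analysis window.** Protocol 3.1 has AEs "considered treatment-emergent from first study drug intake until 28 days after drug discontinuation", and Protocol 7.2.5 agrees. SAP 6.1 sets the residual effect period at 28 days. SAP 7.8.1 closes the double-blind window on the day before open-label nintedanib starts or at "last double-blind drug intake + residual effect period, whichever is earlier".

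**Denominator.** In SAP 7.8.1.2, "The end of time at risk is defined as the minimum of" four dates: the period end including the residual effect period, last contact, death and database lock. The dates that feed last contact in SAP 5 include the "vital status date (from the vital status eCRF page if the patient is known to be alive").

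**Other contacts.** Protocol 3.3.4.1 and 6.2.3 seek vital status at 24 weeks, at 52 weeks and at the end of the trial. Protocol 6.2.3 also schedules a Follow-up Visit with AE review 28 days after the end of treatment for everyone not entering the extension trial. Flow Chart footnote (***) describes that follow-up period only for patients who completed treatment.

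**The concern.** The period over which AEs must be reported and the period over which they are analysed do not match for this subgroup. An unreported event in the residual effect period cannot be told apart from no event, and the SAP has no rule that flags the patient or adjusts the rate.

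The placebo-controlled comparison of AEs is a main reason for the design (Protocol 3.2), and the arms are small, about 20 and 10. One nintedanib patient more or fewer in a table row is 1/20 = 5 percentage points. The reduced rule also depends on the investigator's judgement of relatedness, in a population where Protocol 1.4.2 reports no experience outside this trial.

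**Working it through.** The plan gives no figure for this, so there is none to reproduce. The check sets the rules side by side and then sizes the gap under stated assumptions.

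**Step 1. What is reportable in the 28 days after the last dose, once the reduced rule applies**

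| Event | Reduced rule (Protocol 5.2.7.2.1) | Treatment-emergent (SAP 7.8.1) |
|---|---|---|
| Death or fatal AE | Reported | Yes |
| Treatment-related SAE or AESI | Reported if the investigator learns of it | Yes |
| Non-fatal SAE judged unrelated | Not required | Yes |
| AESI judged unrelated | Not required | Yes |
| Other non-serious AE | Not required | Yes |

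**Step 2. Do those days stay in the denominator?** Take a child without the AE in question whose last dose is on day T. If vital status is later obtained at week 24 (day 169), last contact is day 169. For T = 28 or T = 84 the residual effect period ends near day 56 or day 112, well before that. The minimum is then the end of the residual effect period, and all 28 days count. If no later contact is made, last contact is the earlier date and time at risk is shortened.

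**Step 3. Share of person-time.** The documents give about 20 nintedanib patients, 24 × 7 = 168 double-blind days and 28 residual days. The number of affected patients k (1, 2 or 4) and the last-dose day T (28 or 84) are assumptions. Reduced reporting is assumed to cover all 28 days, which is the worst case.

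For one such patient the share is 28/(T + 28): 28/56 = 50% for T = 28, and 28/112 = 25% for T = 84.

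For the arm the share is 28k / [(20 − k) × 168 + k(T + 28)]:

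| k | T = 28 | T = 84 |
|---|---|---|
| 1 | 28/3,248 = 0.86% | 28/3,304 = 0.85% |
| 2 | 56/3,136 = 1.79% | 56/3,248 = 1.72% |
| 4 | 112/2,912 = 3.85% | 112/3,136 = 3.57% |

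**Step 4. Patients whose new event would be missed.** The documents give no AE rate. Assume a first-event rate r for a given AE of 0.5 to 4 per patient-year. The chance of an event in 28 days is 1 − exp(−28r/365.25), which is 3.8% at r = 0.5 and 26.4% at r = 4. Multiplying by k gives the expected number missed if the event type is not reportable: 0.04 to 0.26 patients for k = 1, 0.08 to 0.53 for k = 2, and 0.15 to 1.06 for k = 4.

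**The case against.** The case on the other side is substantial.

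- **Timing.** The reduced rule is undated. Early stoppers are asked to attend the End of Treatment visit as soon as possible, and AEs are reviewed there (Flow Chart). A family that attends it, or that refuses visits only later, loses part of the window or none of it.
- **Competing text.** The general rule in 5.2.7.2.1 and the Follow-up Visit in 6.2.3 both point to full collection. The vital-status paragraph does not say that the general rule lapses.
- **Pharmacology.** With a terminal half-life of 7 to 19 hours (Protocol 1.2), five half-lives end by 95 hours, about day 4. Deaths remain reportable throughout, as do related SAEs and AESIs that become known.
- **Counting.** The primary safety endpoint counts each patient once, so a child with an earlier AE is already in it. Time at risk for a specific AE stops at its first onset, so an AE that began before drug was stopped gains no residual days.

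All of this limits the size and stands. It does not remove the mismatch. The two collection rules conflict, the Follow-up Visit is a physical visit that these families may refuse, and the plan itself assigns 28 days, not four, to treatment.

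A reader might also infer that reporting always shrinks on the day of the last dose, or that intolerance concentrates the loss on nintedanib. The documents support neither: the start is not dated, and nothing shows who would decline visits or in which arm.

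**Conclusion.** The point holds as an inconsistency between the collection rule and the analysis window, and within the collection rules themselves. For early stoppers who decline visits, three kinds of treatment-emergent event could be missed in the residual effect period: non-serious AEs, non-fatal unrelated SAEs and unrelated AESIs. The denominator mismatch arises only where a later contact, such as vital status, exists.

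The size is probably small and cannot be derived from the documents. The person-time shares above rest on assumed numbers of patients and on the worst case for when reporting is reduced. The effect falls mainly on the system organ class and preferred term tables, the tables of SAEs and AESIs (through those judged unrelated), and the exposure-adjusted rates. A reader might infer material bias in the primary any-AE percentage. That does not follow, because only a child with no earlier AE in the double-blind window could change it.

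**What to change.** In Protocol 5.2.7.2.1, state that all AEs are collected until 28 days after the last dose, by telephone if visits are declined, and that reduced reporting starts only after that. Align this with the Follow-up Visit text in 6.2.3 and with Flow Chart footnote (***), so that it is clear who has that visit and what replaces it for families who refuse.

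The cost is a few sentences and one telephone contact for a few families who have already agreed to be contacted. A call will not detect findings that need laboratory tests or imaging, so some AESIs would still be missed.

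Do not shorten time at risk for all AEs in these patients. Deaths and reported related SAEs and AESIs in the residual effect period would still count in the numerator, so a shorter denominator would inflate their rates. At most, where the day-28 contact is not made, add a sensitivity analysis to SAP 7.8.1.2. It would end time at risk at the last full AE assessment only for the event types no longer collected, and keep the residual effect period for deaths and related SAEs and AESIs.
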